## 12.4.2 Annual review

The Lead Principal Investigator must report study progress (e.g., the number of subjects enrolled, status of AEs, protocol deviation, etc.) to the Certified Review Board at least once a year , and have the Certified Review Board review and approve the continuation of this study.

In South Korea and Taiwan, the principal investigator must report to the Ethical Review Board at least once a year of the study progress, and have the Ethical Review Board review and approve the continuation of this study.

## 12.5 Disclosure of study-related information

This study will be registered in ClinicalTrials.gov, Japan Registry of Clinical Trials (jRCT), and UMIN Clinical Trial Registration (UMIN-CTR) to disclose its information.

## 12.6 Handling of inquiry from subjects and related parties

If a staffer other than principal investigator/sub-investigator receives an inquiry from subjects or related party, such staffer will promptly contact the principal investigator or sub-investigator, and the inquiry will be handled by the principal investigator or sub-investigator, or as necessary by the Lead Principal Investigator.

#### 12.7 Conflicts of interest

This study is a collaborative research conducted by Keio University School of Medicine and Eisai Co., Ltd., the distributor of Humira® and funded by Eisai Co., Ltd. under a collaborative research contract between the parties that define the responsibilities of each party. While this study is conducted based on the specified responsibilities and roles, Eisai Co., Ltd. shall not be involved in data management including database access during the study as well as statistical operation so as to prevent possible bias of the study results; provided that Eisai will be involved in the preparation of and changes to the protocol (including statistical analysis plan), approval of the clinical study report, and delivery of relevant information. Pfizer Japan Inc., the marketing authorization holder of Rheumatrex® and AbbVie GK, the marketing authorization holder of Rheumatrex.

Also, necessary information concerning conflicts of interest associated with principal investigators/sub-investigators and Study Biostatistician of this study and Eisai Co., Ltd., AbbVie GK, and Pfizer Japan Inc. will be disclosed to a department in charge of the management of conflicts of interest at each study site and then will be appropriately managed. Furthermore, in Japan, the conflicts-of-interest management plan will be reviewed by the Certified Review Board in accordance with the Clinical Trials Act.

#### 12.8 Handling of subjects after end of study

Treatment after completion and discontinuation of this 48-week study will not be specified.

#### 12.9 Handling of important findings concerning genetic characteristics, etc.

Genetic characteristics will not be analyzed in this study, and thus, important findings thereto related are not anticipated.

# 12.10 Retention and future research use of clinical samples, and transfer thereof to other research facilities

Investigational blood samples collected in this study will be retained at an external laboratory until study completion, and in principle all be disposed of immediately upon study completion;

However, upon a separate consent of subjects and approval of Certified Review Board, the clinical samples will be retained in Keio University for future research use for 5 years from the date of study completion report or 3 years from the publication of study results, whichever comes later, and may be transferred to other research facilities as necessary.

## 13 Handling of data, and retention of record

## 13.1 Handling of data

In this study, subject ID will be issued through IWRS, and all data except for SAE report will be collected through EDC. The principal investigator or sub-investigator will enter data in EDC promptly upon completion of the evaluation/assessment in each subject.

Based on a separate data management plan, the data center shall send reminders for overdue data, investigate the data and generate data clarification, correct the data according to the data clarification, manage the database, and also, prepares a dataset for statistical analysis based on the data entered in the database.

## 13.2 Retention of records

Principal investigator shall appropriately retain the data and records concerning this study for at least 5 years from the date of study completion report or 3 years from the last publication date of study results, whichever comes later.

# 14 Economic burden on subjects, and insurance and other measures14.1 Economic burden on subjects

The medical cost associated with this study including that for drugs and tests (except for offlabel use of special tests) during the study will be paid in accordance with each country's healthcare scheme. In Japan, the study treatment to be provided is within the scope of general clinical practice using the approved drugs, and the cost will be paid by the health insurance and subjects.

Reward for subjects to take part in this study shall be paid in accordance with each country's rule.

#### 14.2 Insurance

Adequate caution shall be in place for treatment of known SAEs. Upon occurrence of an AE during this study, the principal investigator/sub-investigator shall promptly take necessary actions (tests, treatment, study discontinuation, etc.) to ensure the safety of the subject, and with technologies covered by the insurance, take initiative in to provide the best available treatment and other procedures for the subject.

The sponsor shall carry a clinical study insurance as a measures to secure the compensation for death and severe impairment (grade 1 or 2) that may occur in this study.

## 15 Publication of study results

Key study results will be published in a journal in English language upon completion of the final analysis. Presentation at academic conferences will be arranged and performed by Lead Principal Investigator, Study Investigational Operator, and Coordinating Investigators. The presenter will be selected by Lead Principal Investigator upon approval of Eisai Co., Ltd.

Prior to the publication of key study results, the data collected before randomization may be analyzed in the course of the study for the purpose of presentations at academic conferences. Also in this case, presentation at academic conferences will be arranged and performed by the Lead Principal Investigator, Study Investigational Operator, and Coordinating Investigators, and the presenter will be selected by the Lead Principal Investigator upon approval of Eisai Co., Ltd.

## 16 Appendix

## 16.1 Criteria for RA

In the past, a set of criteria released in 1987 has been used widely, but in order to facilitate early diagnosis and early treatment, a new set of criteria was released in 2010. In this study, those meeting 1987 revised ACR criteria or 2010 ACR/EULAR criteria are considered as RA.

## 16.1.1 ACR revised criteria (1987)

- [1] Morning stiffness of  $\geq 1$  hour for  $\geq 6$  weeks
- [2]  $\geq$ 3 swollen joints for  $\geq$ 6 weeks
- [3] Swollen wrist joint, metacarpophalangeal (MCP) joint, or proximal interphalangeal (PIP) joint for ≥6 weeks
- [4] Symmetrical swollen joint for  $\geq 6$  weeks
- [5] Radiological findings of bone erosion typical with RA, or clear bone decalcification in the hands
- [6] Rheumatoid nodule (subcutaneous nodule)
- [7] Rheumatoid factor positive

A condition meeting 4 of the above 7 is categorized as RA.

## 16.1.2 ACR/EULAR criteria (2010)

Patients meeting both of the following criteria will be applicable, and scored accordingly.

- 1) At least one joint with definite clinical synovitis (swelling)
- Synovitis is not better explained by another disease Scoring: ≥6 points = Definitive RA
  - A. Joint involvement

	• 1 large joint	0 points
	• 2 - 10 large joints	1 point
	• 1 - 3 small joints (with or without involvement of large joints)	2 points
	• 4 - 10 small joints (with or without involvement of large joints)	3 points
	• $\geq$ 11 joints (at least 1 small joint)	5 points
B.	Serology (at least 1 tests result is needed for classification)	
	• Negative RF and negative anti-CCP antibody	0 points
	Low-positive RF or low-positive anti-CCP antibody	2 points
	• High- positive RF or high-positive anti-CCP antibody	3 points
C.	Acute-phase reactant (at least 1 tests result is needed for the classification	on)
	Normal CRP and normal ESR	0 points
	Abnormal CRP or abnormal ESR	1 point
D.	Duration of symptoms	
	• <6 weeks	0 points
	• $\geq 6$ weeks	1 point

8.3.	Plasma Micro RNA at Week 24	10		
8.4.	Serum Anti-adalimumab Antibody at Weeks 24 and 48			
9. Re	vision History	11		
9.1.	Revision from Protocol	11		
9.2.	Revision History of the Statistical Analysis Plan			
10. Organization and Environment for Statistical Analyses				
10.1.	Study Biostatistician	11		
10.2.	10.2. Person in Charge of Statistical Analysis			
10.3.	Software Environment	11		
11. Sig	nature	12		

1. Objectives of the Specified Clinical Trial

This study is intended to evaluate the optimal dosage of methotrexate (MTX) as an addon therapy to adalimumab (ADA) in patients with rheumatoid arthritis (RA) who do not achieve remission by MTX monotherapy, and to measure erythrocyte MTXpolyglutamates (MTX-PG) concentration to evaluate its relation to the efficacy and safety of MTX therapy in RA patients.

- 1.1. Primary Endpoint
- SDAI remission rate at Week 48 in concomitant ADA MTX maximum tolerable dose extended treatment group and concomitant ADA MTX dose reduction group

1.2. Secondary Endpoints

[Efficacy]

- · SDAI remission rate at Week 24
- \cdot SDAI remission rate at Week 48 in MTX monotherapy group
- Percentage of disease activity category by SDAI, CDAI, DAS28-ESR and DAS28-CRP at each assessment timepoint
- SDAI, CDAI, DAS28-ESR, and DAS28-CRP at each assessment timepoint, and change from baseline to each assessment timepoint
- · ACR20, ACR50, and ACR70 response rate at each assessment timepoint
- Tender joint count, swollen joint count, VAS (physician- and patient-reported), HAQ, CRP, ESR, MMP-3, RF, and anti-CCP antibody at each assessment timepoint, and change from baseline and Week 24 to each assessment timepoint
- Modified total sharp score (mTSS) at each assessment timepoint, and change from baseline to each assessment timepoint
- · Structural remission (mTSS ≤0.5) rate at each assessment timepoint
- \cdot HAQ remission rate at each assessment timepoint

[Safety]

- Vital signs and laboratory values at each assessment timepoint, and change from baseline to each assessment timepoint
- Status of AE (Up to Week 24, and up to Week 48 for each ARM)
- 1.3. Exploratory Endpoints
 - Erythrocyte MTX-PG concentration at Weeks 0, 4, 8, 12, 24, 36, and 48
 - Blood cytokine (IL-6, VEGF) at Weeks 0, 24, and 48
 - Plasma micro RNA at Week 24
 - · Serum anti-adalimumab antibody at Weeks 24 and 48

2. Considerations for Statistical Analysis

2.1. Data Evaluation

The interim analysis will not be conducted in this study. However, prior to the final analysis, the data obtained before randomization will be summarized in the course of the study for the purpose of presentations at academic conferences. The summary of the data is allowed to be presented at academic conferences after the completion of subject enrollment in principle. This study will not be biased as the data obtained before randomization are collected.

2.2. Data Monitoring

Monitoring will be performed on this study to ensure the compliance with the study protocol, accurate data collection, appropriate informed consent process, and adequate safety assurance of subjects.

Monitoring will include central monitoring of EDC data and on-site monitoring, both of which will be conducted in accordance with the monitoring plan to be separately set out.

2.3. Handling of Study Data

- · Fixed data after the completion of follow-up will be used for statistical analyses.
- For subjects who were enrolled more than once, statistical analyses will be conducted by removing the data that became unnecessary.
- Data handling meeting will be held prior to the database lock to discuss and determine how to handle individual data after removing the information on which treatment arm each subject was randomized to.
- For clinical laboratory values that exceed or fall below detection limits, detection limits will be substituted for actual values.
- As a rule, baseline is defined as Week 0. If the value at Week 0 is missing or not measured, the time of screening is regarded as baseline.
- · Change and percentage change are defined as follows:

Change = measured value after intervention – measured value at baseline Percentage change = (change/measured value at baseline) x 100 (%)

- 2.4. Handling of Missing Values
 - Subjects with missing data at an assessment time point of SDAI remission, ACR20, ACR50, and ACR70 response, HAQ remission, and structural remission due to study discontinuation or other relevant reasons will be considered as a "non-responder" at the time point of missing data.
 - Subjects with missing data at an assessment time point of CDAI, DAS28-ESR, DAS28-CRP remission due to study discontinuation or other relevant reasons will be considered as a "non-responder" at the time point of missing data.
 - Any missing data on SDAI, CDAI, DAS28-ESR, and DAS28-CRP will be considered as missing at the time point of missing data.

If there is a missing data on the assessment of SDAI, CDAI, DAS28-ESR, DAS28-CRP, and mTSS, the sensitivity analysis of GEE or MMRM method will be performed. If the result does not converge, a missing data will be imputed with the last observation carried forward (LOCF). In addition, for the sensitivity analysis of primary endpoint, a missing data on the final scheduled visit will be imputed with data on End of Study.

2.5. Variable Transformation

If the distribution of measured values is largely deviated from the normal distribution, variable transformation will be conducted such as logarithmic transformation where necessary.

2.6. Significance and Confidence Levels

The analysis on non-inferiority will be performed with a two-tailed confidence interval of 90%. A two-tailed significance level of 5% with a two-tailed 95% confidence interval will be used for all other analyses unless specified otherwise.

2.7. Descriptive Statistics

Descriptive statistics (number of subjects, mean, standard deviation, minimum, median, and maximum as continuous variables, and number and proportion [%] of subjects as nominal variables) will be computed.

2.8. Multiplicity Adjustment

Multiplicity will not be adjusted in this study.

3. Statistical Analysis Set

- 3.1. Definition of Statistical Analysis Set
- 3.1.1. Full analysis set (FAS)

FAS is defined as a group of subjects who receive study drug (MTX) and have evaluable efficacy data at 1 or more time points following the administration of study drug (including subjects who discontinued the study before Week 24 as well as those randomized to ARM-1, 2 or 3).

Modified FAS (mFAS) is defined as a group of subjects who are randomized after Week 24, receive study drug (ADA), and have evaluable efficacy endpoint at 1 or more time points following the administration of study drug (only the subjects randomized to ARM-2 or 3).

3.1.2. Per protocol set (PPS)

PPS is defined as a group of subjects among mFAS who adequately complied with the protocol after excluding subjects with the following significant protocol deviations, e.g. study procedures, concomitant medications (only the subjects randomized to ARM-2 or 3).

Deviation from the inclusion/exclusion criteria

- · Deviation from the discontinuation criteria
- · Deviation from prohibited concomitant therapies
- · Subjects without follow-up data
- Subjects with the study drug compliance of <75%

3.1.3. Safety analysis set

The Safety Analysis Set is defined as a group of subjects who receive study drug (MTX) and have evaluable safety data at 1 or more time points following the administration of study drug (including subjects who discontinued the study before Week 24 as well as those randomized to ARM-1, 2 or 3).

3.2. Statistical Analysis Set for Each Endpoint

The analysis of primary efficacy endpoint will be performed on mFAS as the main analysis set, and on PPS as a supplementary analysis set. All other efficacy and exploratory analyses will be performed exclusively on FAS. Meanwhile, the analysis of safety variables will be performed on the Safety Analysis Set.

4. Analysis Plan of Subject Disposition and Overall Exposure

4.1. Subject Disposition

The following numbers will be calculated: Number of subjects enrolled; number of subjects who received the study drug (MTX), number of subjects with evaluable/non-evaluable SDAI at Week 24; number of subjects included in the Safety Analysis Set; number of subjects included in FAS. In addition, the following numbers will also be calculated: Number of subjects who withdrew the informed consent; number of subjects who had not received any study drug after enrollment, number of subjects without any data on the primary endpoint; number of subjects who did not meet the inclusion criteria; number of subjects who met the exclusion criteria.

Of subjects who satisfied the criteria for SDAI remission at Week 24 and were randomized to ARM-1, the number of subjects who did/did not have SDAI remission at Week 48, number of subjects included in the Safety Analysis Set, and number of subjects included in FAS will be calculated. Furthermore, the number of subjects who had not received any study drug after Week 24, and number of subjects without any data on the primary endpoint at Week 24 onward will also be calculated.

Of subjects who did not achieve SDAI remission at Week 24, the following numbers will be calculated for ARM-2 and ARM-3, respectively: Number of subjects randomized; number of subjects who did/did not achieve SDAI remission at Week 48; number of subjects included in the Safety Analysis Set, FAS, mFAS, and PPS, respectively. In addition, the number of subjects who had not received any study drug after randomization, and number of subjects without any data on the primary endpoint after randomization, will also be calculated.

4.2. Summarizing Discontinuations

The number of subjects who discontinued the study before Week 24, or at Week 24 onward will be summarized with the reasons for discontinuations for each ARM in FAS, mFAS, PPS, and the Safety Analysis Set, respectively, and prepare a list (subjects who discontinued the study before Week 24 as well as subjects randomized to ARM-1, 2, or 3 included in FAS and the Safety Analysis Set; only the subjects randomized to ARM-2 or 3 included in mFAS and PPS).

4.3. Statistical Analysis Set for Each Analysis

The analysis of primary efficacy endpoint will be performed on mFAS as the main analysis set, and on PPS as a supplementary analysis set. All other efficacy and exploratory analyses will be performed exclusively on FAS. Meanwhile, the analysis of safety variables will be performed on the Safety Analysis Set.

4.4. Exposure to MTX

Descriptive statistics of MTX oral dose during each treatment week will be computed. In addition, descriptive statistics will be computed by country for each ARM.

5. Analysis Plan of Demographic Characteristics

The distribution of subjects' demographic characteristics and descriptive statistics will be calculated for each ARM in FAS, mFAS, PPS, and the Safety Analysis Set, respectively (subjects who discontinued the study before Week 24 as well as subjects randomized to ARM-1, 2, or 3 included in FAS and the Safety Analysis Set; only the subjects randomized to ARM-2 or 3 included in mFAS and PPS). The data will be compared between ARM-2 and ARM-3 in each analysis set using chi-square test for nominal variables (Fisher's exact test as needed), Wilcoxon rank sum test for ordinal variables, and t-test for continuous variables.

6. Efficacy Analysis

6.1. Analysis Plan of Primary Endpoint

The primary analysis for this study is intended to demonstrate the non-inferiority of ADA/MTX-reduced dose group (ARM-3) to ADA/MTX-MTD group (ARM-2) in terms of the primary endpoint, that is, SDAI remission rate at Week 48. The adjusted intergroup risk difference and its two-tailed 90% confidence interval in terms of SDAI remission rate at Week 48 will be calculated by Mantel-Haenszel test with country as a stratification factor to verify non-inferiority of ARM-3 to ARM-2 with the non-inferiority margin of -15%. As a sensitivity analysis, point estimates and their 95% confidence interval for changes in SDAI remission rate from baseline to each assessment timepoint will be calculated by generalized linear mixed model (Breslow NE, Clayton DG, J Am Stat Assoc 1993;88(421): 9-25, Wolfinger RD, O'Connell MA, J Stat Comput Sim 1993; 48: 233-243.). Unstructured

will be selected as a correlation structure, and if the analysis does not converge, Toeplitz, Autoregressive, Compound-symmetry structure will be used in order.

In addition, a missing data on the final scheduled visit will be imputed with data on End of Study to assess SDAI remission rate.

Furthermore, multiple logistic regression analysis will be conducted to assess potential effects of each explanatory variable on the response variable with SDAI remission/non-remission at Week 48 as the response variable, and age, sex, autoantibody profile, SDAI score at screening, change in mTSS from screening to Week 24 as explanatory variables, for which a model to minimize the AIC is to be adopted in principle by choosing appropriate variables.

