## 4.3 Bias

#### 4.3.1 Randomization

If a subject does not achieve to clinical remission (SDAI  $\leq$ 3.3) at Week 24 despite the maintenance of MTX dose at  $\geq$ 10 mg/week, the subject will start receiving ADA as an add-on therapy. Subjects then will be stratified by countries (Japan, South Korea, and Taiwan) as a stratification factor, and for each stratum, subjects will be randomized at a 1:1 ratio to either a group in which the MTD of MTX (10 to 25 mg/week) will be maintained (ARM-2), and a group in which the dosage of MTX will be reduced to 6 to 8 mg/week (ARM-3). Upon completion of Week 24 assessments, principal investigator/sub-investigator shall enter the Week 24 dosage of MTX, tender joint count (28 joints), swollen joint count (28 joints), VAS (physician- and patient-reported; 10 cm scale), and CRP in IWRS. If all necessary information is entered, a relevant treatment group in line with the status of randomization (ARM-1, ARM-2 or ARM-3) will be issued by IWRS.

The MTX dosage shall be either 6 mg/week or 7.5 mg/week in subjects in ARM-3 whose maintenance dose of MTX at Week 24 is 10 mg/week.

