## 9.2.1.1 Method of analysis for primary efficacy endpoint

The primary analysis for this study is intended to demonstrate the non-inferiority of ADA/MTX-Reduced Dose Group (ARM-3) to ADA/MTX-MTD Group (ARM-2) in terms of the primary endpoint, that is, SDAI remission rate at Week 48. The intergroup difference in the SDAI remission rate and its two-tailed 90% confidence interval will be calculated based on a stratified analysis with country as a factor in mFAS as the main statistical analysis set. The non-inferiority margin shall be -15%.

Moreover, a multivariate statistical analysis on the SDAI remission rate at Week 48 will be performed for the following variables; age, gender, autoantibody profile, SDAI at screening, and change in mTSS from screening to Week 24.

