#### 9.4 Number of subjects

• Target number of subjects to be enrolled

300 subjects (target number of subjects to be enrolled in each study site is shown in the list of study sites.)

• Randomization ratio

Subjects will be stratified by countries (Japan, South Korea, and Taiwan) as a stratification factor, and for each stratum, randomized to ARM-2 and ARM-3 at the ratio of 1:1.

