## 9.4.1 Sample size selection

Assuming that the SDAI remission rate is 30% for both ARM-2 and ARM-3, and the noninferiority margin is -15%, the number of subjects required for the lower bound of a twotailed 90% confidence interval for the intergroup difference in SDAI remission rate to exceed the non-inferiority margin at 80% power of detection would be 220 subjects in total (110 in each group).

Past reports suggest that the remission rate of MTX monotherapy is about 15%. Also, it has been reported that about 10% of patients cannot continuously receive MTX  $\geq$ 10 mg/week (Atsumi T, et al. 2016: 75-83). Thus, in order to randomize 220 subjects between ARM-2 and ARM-3, 288 subjects need to be enrolled, and considering some dropouts, a sample size of 300 subjects was selected as the target number of subjects to be enrolled.

<Justification for the estimated SDAI remission rate in ADA/MTX-Reduced Dose Group (ARM-3)>

The estimated SDAI remission rate in ARM-3 was calculated in reference to the results of the MTX Monotherapy  $\rightarrow$  ADA+MTX Group in HOPEFUL 1 Study in which Japanese MTX naïve patients receiving ADA+MTX or MTX alone for 26 weeks, and then, all subjects receiving ADA+MTX for another 26 weeks (Takeuchi T, et al. 2014: 536-43). Since the maximum dosage of MTX in HOPEFUL 1 Study was 8 mg/week (6.6±0.8 mg/week: Mean±SD), the results cannot be directly extrapolated to this study in which the maximum dosage of MTX up to Week 24 will be 16 mg/week; yet, the results would be appropriate to use as a reference for the SDAI remission rate in ARM-3 in which the dosage of MTX will be reduced to 6 to 8 mg/week from Week 24 onward. ARM-3 is designed for patients who have not achieved to SDAI remission at Week 24; thus, assuming that the subjects with SDAI remission at Week 26 in HOPEFUL 1 Study (20 subjects = 163 subjects × 12%) remain to be remission at Week 52, the Week-52 SDAI remission rate among the subjects with SDAI non-remission at Week 26 was calculated to be 31.5% [45/143 subjects, that is (65 subjects - 20 subjects)/(163 subjects -20 subjects)]. Therefore, the SDAI remission rate in ARM-3 was assumed to be 30%.

<Justification for the estimated SDAI remission rate of  $\leq$ 3.3 in ARM-2 (ADA/MTX-MTD Group)>

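### The primary risk difference adjusts for country only, and no planned analysis gives a treatment effect adjusted for Week 24 SDAI, which is known before allocation; the gain from adjusting is nil to modest.

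*SAP*

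**What the plan says.** - **Primary analysis.** SAP 6.1: the Week 48 risk difference and its two-tailed 90% CI "will be calculated by Mantel-Haenszel test with country as a stratification factor to verify non-inferiority of ARM-3 to ARM-2". Protocol 9.2.1.1 likewise names country as the only factor, in mFAS, with a margin of -15%.
- **Data held before allocation.** Protocol 4.3.1: once the Week 24 assessments are complete, the investigator "shall enter the Week 24 dosage of MTX, tender joint count (28 joints), swollen joint count (28 joints), VAS" (physician and patient) and CRP in IWRS. The arm is issued only when these are entered. They are the components from which protocol 7.2.4 calculates SDAI.
- **Who is randomised.** Only subjects with Week 24 SDAI above 3.3 who are still on at least 10 mg/week of MTX, 1:1 within country (protocol 4.3.1 and 9.4).
- **Other analyses of the primary endpoint in SAP 6.1.** The first is a generalized linear mixed model of change in remission rate from baseline by visit, with 95% CIs and no named covariates. The second repeats the remission assessment with end-of-study data imputed for a missing final visit. The third is a multiple logistic regression with "age, sex, autoantibody profile, SDAI score at screening, change in mTSS from screening to Week 24 as explanatory variables", reduced by AIC. Its list contains no arm, no country and no Week 24 SDAI.

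**The concern.** The trial is randomised at Week 24, so Week 24 SDAI is the natural baseline for remission at Week 48. If it is prognostic, leaving it out gives a wider interval than the data require. A chance difference between the arms in Week 24 disease activity would also pass into the point estimate with no pre-specified estimate that corrects for it.

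The other planned models do not fill the gap. The mixed model takes Week 0 as baseline (SAP 2.3) and lists no covariates. Because every randomised subject is a non-remitter at Week 24, the binary Week 24 outcome cannot separate a subject just above 3.3 from one with high disease activity. The logistic model uses SDAI from screening, before the 24 weeks of MTX, and cannot give a treatment effect because it has no arm term.

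This matters because the non-inferiority test has little power to spare.

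**Working it through.** **Inputs from the documents.** Remission 30% in both arms, margin 15 points, 80% power, 110 per arm (protocol 9.4.1); two-tailed 90% CI, so z = 1.645 (SAP 2.6); 1:1 allocation (protocol 9.4).

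**Input not in the documents.** R2, the share of variance in Week 48 remission explained by Week 24 SDAI among randomised subjects. It is assumed over a range that starts at zero.

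**Step 1: the plan's own figure.**
- n per arm = 2 x 0.30 x 0.70 x (1.645 + 0.842)^2 / 0.15^2 = 115.4, so 116 (232 in total), against the stated 110 (220).
- At 110 per arm, SE = sqrt(0.42/110) = 0.0618. Power = Phi(0.15/0.0618 - 1.645) = 78.3%. A Farrington-Manning calculation gives 78.5% and an exact calculation for the Wald interval 78.8%. The stated 80% is thus met to within two points.
- Half-width of the 90% CI = 1.645 x 0.0618 = 10.16 points. With no true difference, the expected lower bound lies 15 - 10.16 = 4.84 points inside the margin.

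**Step 2: effect of adjustment, by formula.** The variance is multiplied by (1 - R2), so power = Phi(0.15 / (0.0618 x sqrt(1 - R2)) - 1.645).

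| R2 (assumed) | Power at 110 per arm | 90% CI half-width (points) | Total N for 80% power |
|---|---|---|---|
| 0 | 78.3% | 10.16 | 232 |
| 0.02 | 79.0% | 10.06 | 228 |
| 0.05 | 80.1% | 9.91 | 220 |
| 0.10 | 82.0% | 9.64 | 208 |
| 0.15 | 83.8% | 9.37 | 198 |

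**Step 3: check by simulation.** 4,000 trials per row, 110 per arm, country shares assumed 70/20/10%, no country effect. Country-stratified Mantel-Haenszel was compared with the standardised risk difference from a logistic model on arm, country and Week 24 SDAI. Odds ratios are per SD, lower SDAI favouring remission.

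| Odds ratio | R2 | Variance ratio, adjusted / M-H | Power, M-H to adjusted |
|---|---|---|---|
| 1.0 | 0 | 1.01 | 79.6% to 78.6% |
| 1.3 | 0.014 | 1.00 | 80.2% to 79.6% |
| 1.5 | 0.033 | 0.98 | 78.9% to 79.7% |
| 2.0 | 0.086 | 0.93 | 79.8% to 81.6% |
| 2.5 | 0.137 | 0.89 | 78.7% to 83.2% |

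The Monte Carlo error of one power figure is sqrt(0.8 x 0.2/4000) = 0.6 points, so comparisons should be made within rows. The one-point drop at an odds ratio of 1.0 reflects a slightly larger estimated SE (0.0618 against 0.0609). The empirical SDs are almost equal (0.0615 and 0.0613).

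**Step 4: chance imbalance.** The arm difference in mean Week 24 SDAI, in SD units, has SE sqrt(2/110) = 0.135. A difference of at least 0.2 SD in either direction has probability 2 x (1 - Phi(0.2/0.135)), about 14%. It shifts the unadjusted risk difference by roughly ln(OR) x 0.21 x (1 - R2) x 0.2:
- OR 1.3: 0.262 x 0.207 x 0.2 = 1.1 points.
- OR 2.0: 0.693 x 0.192 x 0.2 = 2.7 points.

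The shift can favour or oppose non-inferiority.

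**The case against.** The strongest case on the other side is that nothing is wrong with the primary test. Randomisation is stratified by country and so is the estimator. The estimate is unbiased under randomisation, its 90% CI is valid, and that CI already allows for chance imbalance. All of this stands. A reader might infer that leaving out Week 24 SDAI biases or invalidates the non-inferiority conclusion; the documents do not support that.

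A reader might also infer that precision is certainly lost. The documents do not support this either: they give no association between Week 24 SDAI and Week 48 remission in subjects who are already above 3.3 and then start ADA. The range has to begin at no gain.

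The logistic model might be read as a failed adjusted analysis. SAP 6.1 presents it as a study of how each listed variable relates to remission, so its missing arm term is not an error in the primary test. It only means that this model cannot supply the adjusted effect.

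Three further points stand in part:
- The thin power is mainly a sample-size matter (110 against 116 per arm). With 300 enrolled and the plan's own losses, 300 x 0.85 x 0.90 = 229.5 would be randomised, giving about 79.8% power before any other dropout.
- Imbalance would be visible, because SAP 6.2.5 summarises SDAI by arm at each visit and SAP 6.2.6 compares activity categories. Seeing it is not the same as having a pre-specified correction.
- Timing matters. The SAP revision is dated July 2021, after the planned end of enrolment in July 2020, in an open-label trial. A late change of primary estimator would invite criticism.

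**Conclusion.** The point holds as one of efficiency and robustness, not validity. A complete, pre-randomisation measure on the outcome's own instrument is collected, and no planned analysis of the primary endpoint uses it to adjust the arm comparison.

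At 110 per arm and 30% remission in both arms, the benefit runs from nothing (R2 near 0, or an odds ratio of about 1.3 per SD) to 5.5 points of power at R2 0.15 (78.3% to 83.8%), with a half-width about 0.8 points narrower (10.16 to 9.37). An R2 of about 0.05, which corresponds to an odds ratio of roughly 1.65 per SD, would restore the planned 80%. These sizes rest on assumed R2 values, the planned remission rates and a normal approximation; the simulation agrees in direction. The change is worth making because it needs no new data, but the primary analysis would remain acceptable without it.

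**What to change.** Before the outcome data are analysed, pre-specify in SAP 6.1, with a matching edit to protocol 9.2.1.1:

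- A logistic model for Week 48 SDAI remission in mFAS with fixed terms for arm, country and continuous Week 24 SDAI, without AIC selection. Week 24 SDAI is calculated by the same rule as the Week 48 score. State its functional form and the variance method in advance.
- A risk difference (ARM-3 minus ARM-2) obtained by standardising the model predictions over all mFAS subjects, with a two-tailed 90% CI compared with the existing -15% margin. The non-responder rule for missing outcomes stays unchanged.
- The country-stratified Mantel-Haenszel risk difference as the supportive analysis. If the primary estimator can no longer be changed, keep Mantel-Haenszel as primary and name the adjusted estimate as supportive.
- For the existing multiple logistic model, either a label that it is prognostic only, or arm, country and Week 24 SDAI as forced terms.

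Cost: edits to the SAP and the protocol, a little more programming, and a delta-method or bootstrap interval in place of a closed formula. If Week 24 SDAI proves unrelated to the outcome, the simulation suggests that power could fall by up to about one point. No new data are needed.
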